6.2.2 Enrollment, Baseline, and/or Randomization

Enrollment

The first study visit will begin with the consent process. At the consent visit, the RC will ask if the candidate would like to read it themselves or have it read to them, then will give the participant time to read the consent (or read it aloud). Then the RC will paraphrase each section of the consent form, and encourage the candidate to ask questions. If the candidate wishes to proceed, they will sign and date the consent form. If there is any concern about comprehension, the RC will administer an adapted 7-item Mini-Mental Status Exam to ensure that there is not cognitive impairment.

The RC will also explain the HIPAA and Medical Records Release forms (if required by the clinical site) to acquire limited data elements from the candidate's medical record. Permission to access medical records is required for participation in the research study. A copy of the forms will be provided to the candidate. A locator form with additional contact information will also be requested, but refusal does not preclude participation in the study.

After informed consent is given, the baseline assessment is completed. On completion of the baseline assessment, the participant will be enrolled and randomized.

Completion status for the consent procedures will be entered in the study database, and signed forms filed in the candidate's name file in a locked filing cabinet, separate from numerical identifiers.

Baseline Assessments

The baseline assessment requires the participant to complete: 1) the Timeline Follow-back Interview to report on substance use over the past 90 days, 2) an online survey (REDCap) to collect a set of baseline-only questionnaires specific to demographics and health history, 3) an online survey using REDCap that collect responses to self-report outcome measures, 4) a toxicology screen involving a urine sample for biochemical evaluation. The administration of the baseline assessment is process takes approximately 1 hour. All assessments will be delivered in a standardized order as outlined below; at baseline only, there are two additional measures on the online REDCap survey

Should a participant be unable to provide data during the scheduled assessment (e.g., unable to provide a urine sample, or unable to complete the assessment in one sitting), research coordinators have up to 14 days to complete the data collection for the assessment.

Baseline, Enrollment, Randomization: Visit 1 (Day 0)

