6.2.3 Blinding

The statistician will be blind to study group. The RC at each facility will not be blind to condition and will inform participants of their study group condition.

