- Brief Pain Inventory (BPI) is a validated, widely used measurement tool for assessing clinical pain.[18] The BPI will be supplemented with a single question on duration of currently reported pain in order to establish whether the pain is acute or chronic.
- Medical Symptoms Checklist will assess self-report of physical symptoms.[19]

Descriptive Data:

- Economic Indicators questions will gather data on employment, health utilization, and legal status.
- Biochemical drug screen will be used to collect point prevalence for substance use on at each assessment time point, and will serve as supplemental data for validation of the TLFB results.
- Adverse Events

Withdrawal of Participants

MABT sessions will be discontinued for any of the following three reasons, but not withdrawn from study (e.g., participant will be continued to be followed for study assessments):

1. Participants are inebriated or high from alcohol or drugs such that they are not able to engage in the intervention on more than one scheduled session.
2. If, in consultation with the participant's healthcare providers, there is concern for his/her safety and well-being (e.g., escalation of symptoms).

A participant could be withdrawn from study if:

If, in consultation with the participant's health care providers, there is sufficient concern for his/her safety and well-being that the participant may be withdrawn and re-directed to more appropriate care. This is described to the participant in the consent process.

If a participant chooses to formally withdraw from the study by notifying the principal investigator, any data collected from the participant will not be used in the analysis.

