8. INTERVENTION DISCONTINUATION

MABT sessions will be discontinued for any of the following reasons, but participant will not be withdrawn from study:

1. Participants are inebriated or high from alcohol or drugs such that they are not able to engage in the intervention on more than one scheduled session.
2. If, in consultation with the participant's healthcare providers, there is concern for his/her safety and well-being (e.g., escalation of symptoms).

The participant could be withdrawn from study if, in consultation with the participant's health care providers, there is sufficient concern for his/her safety and well-being that the

participant may be withdrawn and re-directed to more appropriate care. This is described to the participant in the consent process.

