Secondary Outcomes For comparison of treatment arms on measures of secondary outcomes, we will have 80% power to detect a minimum difference of 0.4 SD. For comparison of medication-assisted treatment retention rates, we hypothesize that retention rates at 12 months will be 60% in the TAU arm and 77% in the MABT arm. The comparison of proportions will have power of 80% to detect this difference. Exploratory Aim: at 6 months after 20% attrition, we expect the total sample to be N = 264 (132 per group) and assume the ability to detect, at minimum, a 15% difference between MABT and TAU groups in proportion of abstinent days. Under these assumptions, the power at 12 months to detect a group difference comparing those using substances at 6 months (nonresponders) in control to those using substances (nonresponders) at 6 months in MABT groups (who have been offered additional sessions) is .65 for a 40% non-responder rate (n = 53 per group). While underpowered, this exploratory aim would provide a reasonable sample size to estimate power for future related research questions and allows us to look at the question of MABT dose and re-engagement for those needing additional treatment support within the primary analysis.

Missing Data: We will evaluate differences in baseline characteristics between participants lost to follow-up versus those who are not. Missing data patterns will also be evaluated including the frequency and percentage of those missing for each variable and the distribution of the number of variables missing. In addition, data collected to the point of lost to follow-up will be compared to the data of those who complete the study to examine possible missing data mechanisms, e.g., missing completely at random (MCAR), missing at random (MAR), or not missing at random (NMAR). Sensitivity analyses will be performed to assess the possible impact of the missing data on the study results. We will consider various methods for missing TLFB including multiple imputation and pattern mixture models.[105] Similar methods will be used for other drug use and opioid craving. We anticipate there should be no missing data for retention since patients who are lost to follow-up are discharged from the program, therefore “missingness” is part of the variable definition.

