9.3 Definition of Populations

Intent-to-treat and dose analyses will be used. Intent to treat analyses includes all participants enrolled in the study. The dose analyses will examine TAU vs. MABT participants who completed > 75% of the initial intervention. Exploratory dose analyses will assess the impact of additional MABT sessions in the subpopulation of MABT-assigned participants who report using substances at the 6 month assessment.

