9.5 Outcomes

9.5.1 Primary Outcome

The primary outcome is patient-reported days of abstinence from illicit opioid use measured at the 6 month endpoint for the R33 and 12month endpoint for the R01. Self-reported substance use is the recommended approach for intervention studies.[97] Days of illicit opioid use is defined as the number of days in which opioids other than MAT (buprenorphine or methadone) are used. Time-Line Follow-Back Interview (TLFB)[3, 4] will be used to assess opioid use, other illicit drugs, marijuana, and alcohol use. Participants will be asked first to identify what substances were used in the previous 90 days at each time assessment point (scheduled every 90 days). The participant will then be asked to use a calendar to retrospectively estimate their substance use, for each of the identified substances. Days of other illicit substance use is defined as the number of days (e.g. cocaine, methamphetamine, hallucinogens, or non-prescribed benzodiazepine) are reported using the TLFB.

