9.5.2 Secondary Outcomes

Measures of mental health (distress symptoms and emotional well-being) will include three well-validated scales for diagnostic screening: the 9-item PHQ-9 to screen for depression[6, 7], the 7-item ($\alpha = .92$) GAD-7 for anxiety[8], and the Posttraumatic Stress Disorder Checklist for DSM-5 (PCL-5),[9] which assesses symptoms of post-traumatic stress on a Likert-type scale with 20 items ($\alpha = .94$). The 4th measure, the Difficulty in Emotion Regulation Scale short form (DERS-SF)[10, 99] assesses difficulties in the modulation of emotional arousal. There are 18 items on a Likert-type scale (DERS $\alpha = .93$; DERS short form α ranges from .78 to .91 with original DERS subscales) and four subscales that assess the degree of awareness, understanding, and acceptance of emotions, and the ability to act in desired ways regardless

of the emotional state. The 5th and 6th measures, the Freiberg Mindfulness Questionnaire (FMQ) with 14 items[14], and the Multidimensional Assessment of Interoceptive Awareness (MAIA)[15] with 32 items on a Likert-type scale are used to assess skills learned in the intervention.

Opioid craving will be assessed using a single item numeric scale.[5] Participants are asked: “On a scale of 0-10, please indicate how much craving you have experienced during the past week,” with responses anchored at “0=no craving at all” and “10-strongest craving ever”. Retention will be defined as days retained in the program, or time to program discharge. Program discharges are documented in the electronic medical record (EMR) and date of discharge will be extracted from the record.

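### Data from formal withdrawers are dropped from the analysis, although intent-to-treat is defined as everyone enrolled

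*Combined protocol and SAP*

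**What the plan says.** Section 6.2.5, under Withdrawal of Participants, sets the data rule for a participant who formally withdraws by notifying the principal investigator: "any data collected from the participant will not be used in the analysis". It applies in either arm and at any time.

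Section 9.3 defines the main population without exception: "Intent to treat analyses includes all participants enrolled in the study". Section 6.2.2 fixes when that status begins: "On completion of the baseline assessment, the participant will be enrolled and randomized".

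Three other places bear on the point:

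- Section 9.5.1 gives the primary outcome as "measured at the 6 month endpoint for the R33 and 12month endpoint for the R01".
- Section 9.2, on ordinary loss to follow-up, plans that "data collected to the point of lost to follow-up will be compared to the data of those who complete the study", and considers multiple imputation and pattern-mixture models for missing TLFB data.
- Section 8 repeats the safety-withdrawal text ("The participant could be withdrawn from study if") but has no sentence on use of the data.

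**The concern.** A formal withdrawer is an enrolled, randomised participant, so sections 6.2.5 and 9.3 both apply and give opposite instructions. An analyst could follow 6.2.5 and analyse all enrolled minus formal withdrawers, but that is not the set section 9.3 calls intent-to-treat.

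The exclusion depends on something that happens after randomisation. It is also chosen by people who know their arm: section 6.2.3 says the research coordinator "will inform participants of their study group condition". If those who withdraw differ in substance use from those who stay, or withdraw at different rates by arm, the comparison can be biased.

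The rule also treats like cases differently. Two participants with the same missed visits are handled in opposite ways if only one notified the principal investigator: one contributes earlier visits and informs the missing-data work, the other contributes nothing, not even baseline.

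Retention is unclear as well. Section 9.5.2 says the "date of discharge will be extracted from the record", and section 9.2 expects no missing retention data. Whether that record counts as data collected from the participant is not stated.

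**Working it through.** **Is there an exception elsewhere?** No. Sections 5.3.1 and 5.3.2 concern leaving medication treatment, after which follow-up continues. Stopping MABT sessions (6.2.5 and 8) explicitly does not end study participation. Section 9.2 covers loss to follow-up. Section 9.6 does not mention formal withdrawal. The trigger is therefore narrow, but the conflict for those it catches is unresolved.

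**What is discarded per person.** Visits fall at weeks 12, 24, 39 and 52 (Table 4 in section 6.1). With each TLFB covering the time since the last assessment (section 3), follow-up days are 84 + 84 + 105 + 91 = 364. For someone who attends on schedule until withdrawing:

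| Withdrawal | Assessments lost | Follow-up TLFB days lost |
|---|---|---|
| Before week 12 | 1 of 5 | 0 |
| Weeks 12–24 | 2 of 5 | 84 (23%) |
| Weeks 24–39 | 3 of 5 | 168 (46%) |
| Weeks 39–52 | 4 of 5 | 273 (75%) |

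The 90-day baseline report is lost in every case. Section 9.5.1 describes a 90-day window at each assessment instead; the shares then become 90/360, 180/360 and 270/360, or 25%, 50% and 75%.

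**Effect at 6 months.** Section 9.2 expects 330 × 0.80 = 264 participants at 6 months, 132 per arm. If one of 132 differs from the mean of the other 131 by a gap g, then

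mean(all) − mean(without that person) = g/132.

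Percent days abstinent runs from 0 to 100, so the ceiling is 100/132 = 0.76 points. Gaps of 20 and 40 points, which are assumptions, give 20/132 = 0.15 and 40/132 = 0.30. Equal numbers and gaps in both arms cancel.

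**Effect at 12 months.** Outcomes after withdrawal are missing under either rule, so keeping earlier visits matters only through the correlation model. In a linear GEE with arm-by-visit means:

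- Independence: no change.
- Exchangeable correlation ρ with k visits kept: the arm mean moves by (share withdrawing) × (pre-withdrawal gap) × b, where b = kρ / (1 + (k − 1)ρ).
- ρ = 0.3 gives b from 0.30 (k = 1) to 0.63 (k = 4); ρ = 0.5 gives 0.50 to 0.80; ρ = 0.7 gives 0.70 to 0.90. These correlations are assumptions.

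**Check of the mechanism.** Assumed inputs: 3,000 per arm, 6% of one arm withdrawing after week 24 (k = 3), a 30-point gap, ρ = 0.5. The expected shift is 0.06 × 30 = 1.80 points at 6 months and 1.80 × 0.75 = 1.35 at 12 months under exchangeable correlation. One simulated data set gave these arm differences:

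| Time and structure | Data kept | Data discarded | Shift |
|---|---|---|---|
| 6 months, both structures | −1.842 | −0.224 | 1.62 |
| 12 months, exchangeable | −1.465 | −0.214 | 1.25 |
| 12 months, independence | −0.214 | −0.214 | 0 |

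A repeat with five data sets of 1,500 per arm gave shifts of 1.80, 1.37 and 0. This confirms how the bias arises; it says nothing about its size in this trial.

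**The case against.** The best defence is that section 6.2.5 is a specific rule for one named event and section 9.3 a one-line general definition. Reading the specific over the general gives a workable set, and one clause in 9.3 would cure the label. That stands as an alternative repair. It does not make the current text consistent, and it leaves observed outcomes discarded by post-randomisation choice.

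The exclusion may honour a consent commitment. The consent pages are not available for this review, so this cannot be checked. Where removal was promised, the data cannot be recovered. Recruitment was also under way before this version, so earlier consent terms matter.

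The impact per person is small. A shift of 0.15 to 0.30 points is about 1% to 2% of the 14-point difference in the power statement (section 9.2), and the prior study's difference was 88.6 − 80.0 = 8.6 points. Several withdrawers in one arm with a large gap would be needed to matter. This is fair.

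The 6-month argument relies on the R33 endpoint in sections 9.2, 9.5.1 and 9.6, whereas the primary hypothesis in sections 1.1 and 9.1 runs to 12 months only. If the R33 analysis precedes a given withdrawal, its result is untouched. The 12-month factor assumes a linear model; section 9.6 plans generalized linear models, with a logit-link GEE as a sensitivity analysis and the correlation structure still to be selected, so the factor is indicative only.

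Finally, section 9.2's use of data up to loss is a missingness diagnostic and does not itself say how those data enter the primary model, and section 8's silence is an omission, not a second conflict. Both points are correct and leave the main conflict in place.

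**Conclusion.** The concern holds and should be fixed. The contradiction between sections 6.2.5 and 9.3 is certain from the text. Its effect on the result is not: the documents give neither a formal-withdrawal rate nor an outcome gap, so the total bias has unknown direction and size and may be near zero. What can be bounded is the 6-month raw mean, at no more than 0.76 points per withdrawer, given 132 per arm and withdrawal after the week-24 visit. At 12 months the gain from keeping data is limited, and nil under an independence structure.

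The main reason to act is that, as written, the analyst must choose between two rules, possibly after seeing data, and a report could call a set intent-to-treat when it is not.

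**What to change.** Replace the sentence in section 6.2.5 with a rule along these lines: data collected up to formal withdrawal are kept and analysed in the randomised arm; later data are treated as missing under section 9.2; data are removed only where the participant asks for this or the consent form they signed promised it.

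Also:

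- state whether retention data from the electronic record are kept after formal withdrawal;
- report formal withdrawals and data removals by arm;
- cross-refer in sections 8 and 9.3;
- if any data must be removed, say in section 9.3 that the analysed set is not all enrolled participants.

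The cost is a short wording change submitted to the IRB as a modification, with no new data collection. Each of the five consent versions in the revision summary must be checked first. Where a signed consent promised removal, those data stay out and only the labelling and the counts by arm improve.

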7. SAFETY ASSESSMENTS

7.1 Specification of Safety Parameters

It is possible that participants may experience anxiety related to questions asked on the questionnaires. For participants who receive MABT, there may be anxiety due to the use of touch in the MABT sessions or the development of a new therapeutic relationship. During the course of the study, interventionists may develop concerns regarding a participant's risk of suicide or harm to self or others, or health concerns such as increased medical symptoms such as pain, or mental health symptoms of severe depression, anxiety, PTSD. Upon entering the study, all participants will be asked to sign a Treatment Information Release Form, which will allow for two-way communication between research and clinical staff to discuss concerns such as those described.

Any medical emergencies, disclosed suicidal ideation, or other urgent concerns for participant safety experienced by the research coordinators or interventionists will be addressed according to the procedures at the clinical site where the participant is seen. Review of these protocols and accessing emergency contact information will be included in the staff training for all study staff. The study staff with the experience will report the event and resolution/follow-up to the principal investigator(s) that day.

7.2 Methods and Timing for Assessing, Recording, and Analyzing Safety Parameters

The pilot project for this study was found to impart minimal risk by the University of Washington IRB, and the protocol for the full trial will be based on the pilot study. Few to no

study-related adverse events are expected. Prior studies of MABT showed no serious adverse events.[83, 85, 86, 89, 93, 94, 104]

7.3 Adverse Events and Serious Adverse Events

For this study, the following standard AE definitions are used:

Adverse event: An adverse event (AE) is any untoward medical occurrence in a subject during participation in the clinical study or with use of the experimental agent being studied. An adverse finding can include a sign, symptom, abnormal assessment (laboratory test value, vital signs, electrocardiogram finding, etc.), or any combination of these

Serious Adverse Event: A serious adverse event (SAE) is any AE that results in one or more of the following outcomes:

- Death
- A life-threatening event
- Inpatient hospitalization or prolongation of existing hospitalization
- A persistent or significant disability/incapacity
- A congenital anomaly or birth defect
- An important medical event based upon appropriate medical judgment

AEs are graded according to the following scale:

Mild: An experience that does not have a major impact on the patient (e.g., is transient, requires no special treatment or intervention, does not generally interfere with usual daily activities). This includes transient laboratory test alterations.

Moderate: An experience that causes the patient some minor inconvenience, but is alleviated with simple therapeutic treatments. The experience impacts usual daily activities. Includes laboratory test alterations indicating injury, but without long-term risk.

Severe: An experience that causes a substantial disruption to the patient's well-being (e.g., requires therapeutic intervention). The experience interrupts usual daily activities. If hospitalization (or prolongation of hospitalization) is required for treatment it becomes an SAE.

The study will use a form specifically for collection of AEs. AEs will be solicited at all participant followup assessment visits with the RC and collected at all intervention visits by the Interventionists. The AE form will have the following attribution scale:

Not related: The AE is clearly not related to the study procedures (i.e., another cause of the event is most plausible and/or a clinically plausible temporal sequence is inconsistent with the onset of the event).

Possibly related: An event that follows a reasonable temporal sequence from the initiation of study procedures, but that could readily have been produced by a number of other factors.

Related: The AE is clearly related to the study procedures.

We will follow the definition and rules for reporting for **unanticipated problems** as required by the UW IRB. An “unanticipated problem” is a problem or event that meets all of the following criteria:

- 1) Unexpected - The harm (or potential harm) is inconsistent with risk information previously reviewed and approved by the IRB in terms of nature, severity, or frequency as well as the characteristics of the study population.
- 2) Related or probably related to participation in the research. Probably related: There is a reasonable probability (more likely than not) that the incident, experience or outcome may have been caused by the procedures involved in the research, or that it is associated with the use of any drug, biologic, or medical device that is part of the research.
- 3) Suggests that the research places (or could have placed) subjects or others at a greater risk of harm than was previously known or recognized.

Unanticipated problems will be reported within the timeframe required by UW IRB (10 business days).

